## 1.6. Randomization

The socio-demographic data (age, gender, education level and income level) of hypertensive patients from the 7th Family Health Center where the study was to be conducted were obtained as a list and found to be similar. Therefore, no stratification was applied in the study while determining the sample of the study. In the first stage of the study, the individuals registered in the 7th Family Health Center and continuing antihypertensive drug treatment were used to determine the hypertensive individuals defined as non-adherent to the treatment (scoring “8 and above”) using the antihypertensive drug treatment compliance scale. This process was continued until the specified sample size (n: 78) was reached. Each individual to whom the scale was applied was given a number from one to 78 according to the application order and a list of orders was created. In the second stage, the participants were assigned to the intervention and control groups from the web page (<https://www.random.org/>) according to the simple randomization method based on the order in the list created. In this assignment, the assignment of the groups was made by an expert in order to ensure blindness.

The flow chart of the control and intervention groups was prepared in line with the guidelines specified in CONSORT 2022 (Figure 1) (Junqueira et al, 2023).

[figure not shown]

Figure 1. CONSORT (2022) Flowchart of the study.

\*ITT analysis

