### **1.3. Universe of the Research and Study Group**

**Universe:** The research population consists of 407 individuals with primary hypertension between the ages of 40-59, registered in Family Health Center No. 7.

**Working group:** In this study, the sample size was calculated before the data collection stage at a 95% confidence level using the "G. Power-3.1.9.2" program to determine the study group. Özpancar's (2013) study, which examined the effect of education given by nurses on

treatment compliance in patients with hypertension, was used for the calculation. According to the data obtained from the study in question, the sample number required for the study was determined as 35 for each group (35 people for the control group + 35 people for the experimental group; 70 people in total) by taking the alpha value of 0.05 for the Mann Whitney U test, the effect size of 0.90, and the theoretical power as 95%. The 10% loss rate in previous studies (Zahr et al., 2019; Dağıstan Aköz, 2022) was taken into account and it was decided to include a total of 78 participants, 39 in each group.

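### Simple randomisation does not guarantee the planned 39 per group, and likeness on the centre's pre-screening list does not establish balance between the arms of the screened 78

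*Protocol*

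**What the plan says.** Protocol section 1.6 (Randomization) starts from a list of the age, gender, education and income of the centre's hypertensive patients. It judges these alike, without figures or a criterion, and concludes: "Therefore, no stratification was applied in the study while determining the sample of the study". Patients on treatment were then screened with the adherence scale until 78 people scoring 8 or more had been found. They were numbered in order and assigned through a random-number web page "according to the simple randomization method based on the order in the list created". No block, equal-size or split-the-list rule is described. Sections 1.6 and 1.8 say that the list was complete before assignment and that someone other than the researcher made the assignment.

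On arm sizes, section 1.3 states that "it was decided to include a total of 78 participants, 39 in each group". The Abstract reports 39 and 39. Section 1.7 implies the same: 36 completers plus 3 leavers, and 35 completers plus 4 leavers.

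On analysis, Protocol section 1.15 and the SAP compare descriptive characteristics with t and chi-square tests, and outcomes over time with a mixed ANOVA. Neither names a baseline covariate or a stratification factor.

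**The concern.** There are two gaps between what is stated and what follows from it.

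First, simple randomisation in its usual sense assigns each person independently, so arm sizes vary. Equal arms of 39 are then an outcome of chance and not a property of the method. A reader cannot tell from the text which mechanism was used, and a randomised trial should make that clear.

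Second, the list describes registered patients before the adherence screen and before any arms existed. Stratification guards against chance differences between two arms of the people actually randomised, and the list is not evidence on that. The four items also leave out the adherence score, the lifestyle score and blood pressure, which are the trial's own outcomes (section 1.9.8).

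What is at stake is chance imbalance at n = 78, and precision, in an analysis that names no baseline adjustment. The screening adherence score was already in hand for all 78 people when they were assigned.

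**Working it through.** **1. The plan's own sample size (section 1.3).** Inputs: "taking the alpha value of 0.05 for the Mann Whitney U test", "the effect size of 0.90", 95% power, 10% loss. Sidedness is not stated.

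- Method: two-sided noncentral t, with n multiplied by the Mann-Whitney efficiency 3/π (normal data assumed). Noncentrality = d × √(m₁m₂/(m₁+m₂)), where m = 3n/π.
- At n = 35 per group, m = 33.4 and noncentrality = 0.90 × √(33.4/2) = 3.68, giving power 95.2%. The smallest n that reaches 95% is 35, so the stated figure reproduces. One-sided versions give 27 to 32 and do not.
- Loss: 35/0.9 = 38.9, so 39 per group; 70/0.9 = 77.8, so 78 in total. Both reproduce.

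**2. Arm sizes if each of the 78 is assigned independently 1:1.** The number in one arm is Binomial(78, 0.5).

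| Split | Probability |
|---|---|
| Exactly 39/39: C(78,39)/2^78 | 9.0% |
| 36/42 or more unequal | 57.2% |
| 34/44 or more unequal (an arm below 35) | 30.8% |
| 30/48 or more unequal | 5.4% |

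A random permutation of the 78 numbers cut in half, or suitable blocks, gives 39/39 with probability 1.

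**3. What unequal arms would cost.** Mann-Whitney power by the method of step 1:

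| Split | No loss | After 10% loss |
|---|---|---|
| 39/39 | 96.9% | 95.2% |
| 34/44 | 96.7% | 94.9% |
| 30/48 | 96.2% | 94.2% |

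Averaged over all splits under simple randomisation, power after 10% loss is 95.0%, against 95.2% at a fixed 39/39.

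**4. Chance imbalance without stratification, with arms fixed at 39/39.**

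- Continuous baseline variable: the SD of the mean difference is √(2/39) = 0.226 SD units. P(difference ≥ 0.25 SD) = 2 × [1 − Φ(0.25/0.226)] = 27%. P(≥ 0.5 SD) = 2.7%.
- Binary factor with an assumed prevalence of 50% (hypergeometric): a difference of 15 points or more has probability 17%, and 20 points or more 7%.
- On the adherence scale, eligible scores run from 8 to 13 (Table 1 and section 1.9.3), so the SD is at most about 2.5 and 0.25 SD at most about 0.63 points. If the six values were equally likely (assumption), the SD is √(35/12) = 1.71 and 0.25 SD is 0.43 points.

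**5. How much reaches the result.** The documents give no baseline-to-follow-up correlation r, so I assume 0.3 to 0.7, with equal SDs.

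- A baseline difference of 0.25 SD shifts an unadjusted T1 or T2 comparison by r × 0.25 = 0.075 to 0.175 SD. It shifts a comparison of change from T0 by (1 − r) × 0.25 = 0.175 to 0.075 SD in the other direction.
- Against the planning effect of 0.90, that is 8% to 19%.

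**6. What stratification and adjustment would gain.** For a roughly normal score, a median-split stratum in the model removes about r² × 2/π of the outcome variance: 0.09 × 0.637 = 6% to 0.49 × 0.637 = 31%. The continuous baseline score removes r² = 9% to 49%.

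**The case against.** The other side has a good deal of force.

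- **The arms were equal.** The documents report 39/39. A reader might infer that the stated method failed, or that it cannot have been used. Neither is supported. A 9% event is not remarkable, and a closed, numbered list assigned in one step is also compatible with drawing half the list at random and loosely calling it simple. I could not see the flow chart (Figure 1). The mechanism is under-described, not shown to be wrong.
- **Unequal arms hardly matter.** This stands. The 31% chance of an arm below 35 shows a mismatch with the plan, not a power failure, because the other arm is then at least 44.
- **The sentence may be about sampling.** Its wording refers to determining the sample, and screening follows directly. Likeness of the source list would be a relevant reason not to stratify the sampling. The ambiguity is real. But the sentence stands under the randomisation heading, and no other reason is given for unstratified assignment. A homogeneous list would also leave less to imbalance on those four items, so it is not wholly uninformative. It is silent on the baseline scores.
- **Unstratified randomisation is valid.** This stands. It is unbiased in expectation, and the test's error rate already allows for chance imbalance. A reader might infer bias from the missing stratification; the documents give no ground for that.
- **The group-by-time term uses T0.** Section 1.13 says this effect was evaluated. It protects only in part, because change scores over-correct when r is below 1 (step 5).

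**Conclusion.** The concern holds in a limited form. Simple randomisation, as named, does not guarantee 39 per group (9.0% for exactly 39/39 under independent assignment). Likeness of four items on a pre-screening list does not establish balance between the arms of the screened 78, least of all on baseline adherence.

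The consequence is chance imbalance and forgone precision: a 27% chance of a baseline difference of at least 0.25 SD at 39/39. Such a difference is worth roughly 0.08 to 0.18 SD in an unadjusted follow-up comparison if r lies between 0.3 and 0.7. It is not bias, and the effect of unequal arms on power is negligible. The binomial figures assume 78 independent 1:1 draws. The power figures assume normal data and two-sided testing. The values of r and the 50% prevalence are assumptions.

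The point still deserves action because a better allocation was available at almost no cost. The list was closed, everyone on it had been scored, and someone other than the researcher made the assignment. Stratifying on the score would therefore not have made assignments predictable to the recruiter.

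**What to change.** **In the plan (or a repeat of this design):**

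- Remove the argument that likeness on the centre's list makes stratification unnecessary.
- Replace simple randomisation with a restricted 1:1 allocation of the closed list of 78, drawn by the same independent expert within strata of the screening adherence score (for example, split at the median) and totalling 39/39. If both strata have an odd number of people, give the two spare places to opposite arms by a random draw.
- Include the baseline score, or the stratum, in the outcome model. If the baseline score is the covariate, T1 and T2 should be the responses, so that T0 is not on both sides of the model. Stratifying on adherence does not balance the other primary outcome, the lifestyle score; adjusting each outcome for its own baseline value covers both.

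**For the trial as conducted:**

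- State the mechanism that produced 39/39: independent draws that happened to be equal, or a permutation of the list and a split. Do not write that a restricted method was used unless the records show it.
- Add an analysis of each outcome adjusted for its baseline value, labelled post hoc if results were already known. The Abstract already reports group differences, and the SAP is dated 20 June 2024, after the T2 data of May 2024.

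**Cost:** a few minutes more for the expert who makes the allocation, and one or two model degrees of freedom. Concealment is unaffected because the list is closed first. For the completed trial the cost is some wording and one extra analysis per outcome; the allocation itself cannot be changed.

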## 1.7. Reasons for Leaving the Study

The study started with a total of 78 participants and ended with “three” from the intervention group and “four” from the control group. After the participants left, the study was completed with a total of 71 patients, 36 from the intervention group and 35 from the control group. The patients who left the study stated the following reasons for leaving the study: “I am very busy, I can no longer spare time for your work” (n=3), “My blood pressure is no longer high, I am better, I want to leave your intervention” (n=1), “I cannot walk or diet, I cannot lose weight, I do not want to fill out your survey” (n=1) (5 patients in total). In addition, a total of 2 patients had to be removed from the study because the phone numbers they provided could not be reached by the researcher.

## 1.8. Blindfold

The patients were invited to the study by the researcher involved in the study and participant registration was carried out until the targeted sample size (78 participants) was reached. During participant registration, the names and contact information of the patients were collected, and it was stated that they would be contacted and called for the process related to the study. When the targeted sample size was reached in the study, participant registration was terminated and a participant list was created. It is essential that those conducting the randomized controlled experimental study and the participants do not know who is in the intervention group and who is in the control group until the study starts (Akın and Koçoğlu, 2017). Using the participant list created for this purpose, random selection and assignment were made by someone other than the researcher in the study. Thus, selection bias was controlled in the study. After the groups were determined, the patients were not blinded since their consent would be obtained for the application to be made to them during the intervention process.

In this study, a blind technique was applied by concealing from the researcher who was in the control and intervention groups until the nursing interventions based on KMT began. However, the researcher was not blinded during the intervention period.

Since the aim of the nursing profession is to produce information related to real-world practice beyond the boundaries of the laboratory, it is stated that the action approach will more accurately reflect nursing practice, however, it is said that blinding in action (pragmatic) experiments can generally be difficult (ethical, practical, etc. reasons) and sometimes even impossible, and in this case, it can be recommended to blind only those who evaluate the outputs and perform data analysis (Akın and Koçoğlu, 2017). For this purpose, in order to prevent bias in the evaluation of the data; statistical analyses of the coded data (A and B) in the prepared database were performed by a statistician, independent of the researcher. After the statistical analyses of the study and the appropriate tables for the results were made and the research report was written, the codings made for the control and intervention groups were explained. Thus, statistician and reporting blinding was performed during the research process. Intention to treat analysis (ITT) was applied to prevent attrition bias due to missing data in the outcome/outcome measurements during the study process after randomization. In this way, selection, attrition, statistical and reporting bias were controlled.

## **1.9. Data Collection Tools**

In collecting the data of the study; Exclusion Criteria Form, Personal Information Form, Antihypertensive Drug Treatment Adherence Scale, Healthy Lifestyle Behaviors Scale (SYBDÖ-II), Blood Pressure Monitoring Form, Telephone Monitoring Form, and Short Message Service Monitoring Schedule were used.

### **1.9.1. Exclusion criteria form**

This form was created according to the exclusion and inclusion criteria of the study in order to determine the participants to be included in the study. The form consists of a total of 7 questions (age, education level, primary hypertension diagnosis, a second chronic disease, pregnancy or breastfeeding, mobile phone use, compliance with antihypertensive drug treatment) and 1 study inclusion criterion.

### **1.9.2. Personal information form**

This form was created by the researchers as a result of a literature review (Hacıhasanoğlu et al., 2012; Erci et al., 2018; Deniz Akan et al., 2020; Republic of Turkey

Ministry of Health, General Directorate of Public Health, 2021). The form consists of a total of 20 questions. 9 of which determine the socio-demographic characteristics of individuals (age, weight, height, gender, marital status, education status, employment status, monthly income, lifestyle) and 11 questions related to hypertension (duration of hypertension diagnosis, number of daily anti-hypertensive drugs used, duration of anti-hypertensive drug use, regular use of hypertension drug/drugs, place where the treatment is followed, family history of hypertension, hypertension-specific diet application status, daily tea/coffee consumption status, smoking status, alcohol consumption status, regular exercise status).

### **1.9.3. Antihypertensive drug treatment compliance scale**

The Turkish validity and reliability of the scale developed by Morisky, Green and Levine was conducted by Demirezen and Nahcivan (Demirezen and Nahcivan, 2006). The scale includes a total of 9 statements that diagnose medication-taking behavior. The first 8 questions are answered as Yes and No, and yes answers are coded as "1" and no answers are coded as "0". The ninth question has the options "1" never/rarely, "2" occasionally, "3" sometimes, "4" usually, and "5" always, and only one option is marked. In the scoring, Yes = 0 points and No = 1 points are evaluated in questions 5 and 6, while Yes = 1 and No is evaluated as 0 in the other questions. The last question, item 9, is a Likert-type and is evaluated between 1 and 5. The Cronbach alpha coefficient of the scale was reported as 0.82 for the entire scale. In the study, the definitions of compliance and non-compliance with antihypertensive drug treatment were determined according to the 80% cut-off point. In this study, Cronbach's Alpha reliability coefficient was found to be 0.674 in the first measurement, 0.797 in the second measurement and 0.748 in the third measurement. In the evaluation of compliance with antihypertensive drug treatment, an increase in score indicates that the individual is "non-compliant". The total scale score varies between '1-13'. Accordingly, individuals who score "1-7" according to the total scale score are defined as compliant with treatment, while participants who score "8 and above" are defined as non-compliant with treatment.

[figure not shown]
### **1.9.4. Healthy lifestyle behaviors scale II**

Healthy behaviors were collected with the "Healthy Lifestyle Behaviors Scale (HLBS-II)". The scale was developed by Walker et al. (1987) and revised again in 1996 (Walker and Hill-Polerecky, 1996). The scale consists of 52 items in total and has 6 subfactors. The subgroups are spiritual development, health responsibility, physical activity, nutrition,

interpersonal relations, and stress management. All items of the scale are positive. The rating is in the form of a 4-point Likert. Never (1), sometimes (2), often (3), and regularly (4) are accepted. The Cronbach Alpha coefficient of the original scale is 0.94 and the Cronbach Alpha values of the subdimensions of the scale vary between 0.79 and 0.87. The scale was adapted to Turkish by Bahar et al. (2008). In the study in question, Cronbach's alpha reliability coefficient was determined as 0.92 and the reliability coefficients of the sub-dimensions of the scale were determined as; Health responsibility 0.77, Physical activity 0.79, Nutrition 0.68, Spiritual development 0.79, Interpersonal relations 0.80, Stress management 0.64. In this study, Cronbach's Alpha reliability coefficient was found as 0.904 in the first measurement, 0.928 in the second measurement and 0.926 in the third measurement. The scale measures health-improving behaviors in relation to the individual's healthy lifestyle. The overall score of the scale gives the healthy lifestyle behaviors score. The lowest score for the entire scale is 52, and the highest score is 208.

#### **1.9.5. Blood pressure measurement**

Blood pressure was measured by the researcher using a calibrated mercury-manual sphygmomanometer (sphygmomanometer-Erka Perfect Aneroid/Germany) and stethoscope. Blood pressure values were evaluated according to the information in the Turkish Hypertension Consensus Report, and individuals with blood pressure values lower than 120/80 mmHg were defined as "well-managed" and individuals with values above this were defined as "poorly managed." The steps followed in blood pressure measurement according to the office blood pressure measurement criteria specified in the Directive on Family Medicine Screening and Follow-up Coefficient, the Turkish Hypertension Consensus Report, and the ACD are shown in Figure 2 (Aydogdu et al., 2019; Official Gazette, 2021; American Heart Association, 2022).

[figure not shown]

Figure 2. Steps followed in blood pressure measurement (Aydogdu et al., 2019; Official Gazette, 2021; American Heart Association, 2022).

Blood pressure measurements were taken a total of three times (between 09:00 and 17:00 on the day of measurement) for the control group and the intervention group, T0, T1 and T2.

#### 1.9.6. Telephone follow-up form

This form includes 1 question to assess whether the SMSs sent by the researcher were read by the patient. As part of the study, confirmation phone calls were made once a week for the first two weeks and twice thereafter to ensure that the messages were received. No information was provided other than the confirmation that the SMS was received.

#### 1.9.7. Short message service tracking chart

This form, prepared by the researcher using literature (Kes, 2017), includes SMS messages created based on KMT, the patient's name, telephone number, and information indicating the date and time the SMS will be sent.

#### 1.9.8. Measuring results

The primary outcomes of this study were the level of compliance with antihypertensive drug treatment and healthy lifestyle behaviors. Secondary outcomes were changes in SBP and DBP levels. Primary and secondary outcomes were assessed at the first month ( $T_0$ ), the end of the third month ( $T_1$ ), and the end of the sixth month ( $T_2$ ).

Preliminary application: After obtaining permissions for the study, 8 hypertensive individuals (10% of the sample) who met the inclusion criteria were provided with data collection tools and an evaluation of the clarity of the questions; no problems were encountered. These 8 individuals were excluded from the sample.

## **1.10. Data Collection**

Pre-test forms were administered to hypertensive individuals who agreed to participate in the study in November 2023, T1 data in March 2024, and T2 data in May 2024 at the ASM and were filled out by the researcher according to the hypertensive individual's self-report.

## **1.11. Implementation Process of the Research**

The research consisted of the creation of nursing interventions (hypertension education materials (education brochure, education presentation) and SMS messages) and research implementation processes.

### **1.11.1. Establishing nursing interventions**

Nursing interventions were based on KMT and consisted of hypertension education and SMS messages prepared to provide hypertensive patients with medication compliance and healthy lifestyle behaviors. The KMT conceptual framework was used to design nursing interventions. KMT is a common framework explaining the use of health-protective behaviors (Rogers, 1983). In order to engage in health-protective behaviors, it is desired for patients to develop protective motivations. According to the theory, protective motivation is formed as a result of patients' assessments of threats related to their current situation and coping with this threat (Rogers, 1983). In this context, the nursing interventions included in our study were prepared in line with the KMT principles of threat assessment (perceived susceptibility, perceived severity), coping assessment (response efficacy, self-efficacy, response costs) and taking action. In line with these principles, the individuals to be included in the training program, the topics to be included in the program, training methods and materials and SMS messages were determined.

